Phase 3 studies of SOF+RBV for 12 or 16 weeks in treatment-naïve and treatment-experienced genotype 3 HCV-infected subjects demonstrated SVR12 rates of 56% and 62%, respectively. Increasing treatment duration to 24 weeks may further improve response rates. In Phase 2 studies of SOF+RBV for 12 or 24 weeks in treatment-naïve genotype 1 HCV-infected subjects, SVR rates have varied from 47% to 84% depending on the study and patient population. In both genotypes 1 and 3, lower doses of RBV have been associated with reduced efficacy of the regimen. Given the safety need for a reduced RBV dose in the current study (Section 1.8), treatment with SOF+RBV will be administered for 24 weeks to maximize efficacy. Subjects with genotypes 1 or 3 HCV infection have been selected for this study since they represent the largest group of HCV-infected individuals in the regions where this study will be conducted and because the 24 week treatment regimen is appropriate. In contrast, genotype 2 HCV-infected subjects have been shown to have high response rates following 12 weeks of SOF+RBV therapy. If SOF+RBV is well tolerated for 24 weeks in patients with severe renal insufficiency, safety for 12 weeks in this smaller HCV population may be inferred.

1.6.2. Cohort 3

To date in subjects with a CLcr > 60 mL/min, LDV/SOF without RBV has an excellent safety profile, with efficacy > 93% in all patient populations {34474}. Cohort 3, in which LDV/SOF for 12 weeks will be the treatment regimen, will generate clinical data in a patient population with a regimen which is the Standard of Care (SOC) for genotype 1.

Phase 3 trials with LDV/SOF demonstrated the addition of RBV to LDV/SOF for the treatment of HCV in genotype 1 subjects did not increase efficacy. As such, Cohort 3 will not include RBV which is of particular benefit for this patient population in which chronic anemia is common; the preliminary data from Cohort 1 with SOF 200mg + RBV indicate that anemia was the most frequent AE and led to increased epoetin use.

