1.8. Rationale for RBV Dose Selection

Ribavirin increases treatment response rates when administered with interferon or PEG. In addition, reducing the RBV dose from 1000-1200 mg/day to 600 or 800 mg/day when given in combination with SOF reduced SVR rates, as did SOF monotherapy. It is therefore desirable to keep RBV as part of the SOF treatment regimen. Since RBV is cleared renally and its main toxicity is hemolytic anemia which is poorly tolerated in patients with advanced renal insufficiency who are usually anemic at baseline and have little bone marrow reserve, the

starting dose of RBV must be substantially lower than 1000-1200 mg/day. For this study, a dose of 200 mg/day has been selected based on investigator input in light of the high frequency of hemotoxicity of RBV and the general desire to optimize the efficacy of the treatment regimen {24149}.

To date there has been no safety signal identified that is attributable to SOF when administered as part of a combination regimen. Furthermore, SOF does not exacerbate the toxicities associated with RBV, most notably hemolytic anemia. Clinical data with SOF in severe renal insufficiency and in subjects requiring hemodialysis is limited to a single dose study in non-HCV infected subjects. No specific safety signals were identified. The current study is designed to assess the safety and efficacy of therapeutic treatment with SOF+RBV in a small number of subjects with severe renal insufficiency.

The potential benefit of successful treatment of HCV in these subjects is substantial. Few patients with severe renal insufficiency can tolerate combination therapy with PEG+RBV due to profound anemia. SVR rates to interferon monotherapy administered for 48 weeks are less than 50%. Interferon-free treatment for 24 weeks could provide substantial improvements in safety, tolerability and efficacy for individuals with chronic HCV infection.

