4.2. Inclusion Criteria

Subjects must meet *all* of the following inclusion criteria to be eligible for participation in this study.

- 1) Willing and able to provide written informed consent
- 2) Male or female, age ≥ 18 years
- 3) Chronic HCV infection documented by either:
 - a) a positive anti-HCV antibody test or positive HCV RNA or positive HCV genotyping test at least 6 months prior to the Day 1 visit, or
 - b) a liver biopsy performed prior to the Day 1 visit with evidence of chronic HCV infection
- 4) Infection with HCV GT 1, 3 or 4 as determined at Screening, as applicable to cohort
- 5) Subjects must have the following laboratory parameters at Screening:
 - a) HCV RNA $\geq 10^4$ IU/mL
 - b) ALT $\leq 10 \times$ the upper limit of normal (ULN)
 - c) AST $\leq 10 \times$ ULN
 - d) Hemoglobin ≥ 9 g/dL
 - e) Albumin ≥ 3.0 g/dL
 - f) Direct bilirubin $\leq 1.5 \times$ ULN
 - g) HbA1c $\leq 10\%$

- h) Creatinine clearance (CL_{cr}) \leq 30 mL/min, as calculated by the Cockcroft-Gault equation {2202} using ideal body weight (IBW).

$$\text{Male: } CL_{cr} \text{ (mL/min)} = \frac{[140 - \text{age (years)}] \times \text{IBW (kg)}}{72 \times S_{cr}}$$

$$\text{Female: } CL_{cr} \text{ (mL/min)} = \frac{[140 - \text{age (years)}] \times \text{IBW(kg)} \times 0.85}{72 \times S_{cr}}$$

S_{cr} = serum creatinine (mg/dL)

Ideal body weight (IBW) is estimated by the following equations:

Males: $IBW \text{ (kg)} = 50 \text{ kg} + 2.3 \text{ kg for each inch over 5 feet}$

Females: $IBW \text{ (kg)} = 45.5 \text{ kg} + 2.3 \text{ kg for each inch over 5 feet}$

- a. Subjects with CL_{cr} 30-40 mL/min are eligible if they have a prior $CL_{cr} \leq 30$ mL/min within 6 months of Screening
- 6) $INR \leq 1.5 \times ULN$ unless subject has known hemophilia or is stable on an anticoagulant regimen affecting INR.
- 7) A negative serum pregnancy test for female subjects of childbearing potential (see [Appendix 2](#) for definition).
- 8) Male subjects and female subjects of childbearing potential (see [Appendix 2](#) for definition) must agree to use protocol specified method(s) of contraception as described in [Appendix 2](#).
- 9) Lactating females must agree to discontinue nursing before administration of study drug.
- 10) Subject must be of generally good health as determined by the Investigator.
- 11) Subject must be able to comply with the dosing instructions for study drug administration and able to complete the study schedule of assessments.

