5.8.3.2. Hematopoietic Growth Factors

Erythropoiesis stimulating agents (ESAs) should not be used during Screening solely to elevate hematology laboratory parameters to facilitate entry into the study. Patients taking ESAs for anemia related to chronic kidney disease may enter the study. Granulocyte colony-stimulating agents and thrombopoietic growth factors should not be used while the subject is receiving study treatment.

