7.2.1. Summaries of Numeric Laboratory Results

Descriptive statistics (n, mean, SD, median, Q1, Q3, minimum and maximum) will be provided for ALT, AST, total bilirubin, alkaline phosphatase, white blood cell (WBC) counts, neutrophils, lymphocytes, hemoglobin, platelets, reticulocytes, creatinine, INR, and creatinine clearance (calculated by the Cockcroft-Gault equation, using IBW) as follows:

- Baseline values
- Values at each postbaseline analysis window
- Change from baseline at each postbaseline analysis window

A baseline laboratory value will be defined as the last measurement obtained on or prior to the date/time of first dose of study drug. Change from baseline to a postbaseline visit will be defined as the visit value minus the baseline value. The mean, median, Q1, Q3, minimum, and maximum values will be displayed to the reported number of digits; SD values will be displayed to the reported number of digits plus 1.

In the case of multiple values in an analysis window, data will be selected for analysis as described in Section 3.8.3.

The number of subjects with hemoglobin < 10 g/dL and < 8.5 g/dL at any postbaseline visits (up to 30 days after the last dose of any study drug) will be summarized.

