15.11.2.2.1	Grade 3 or 4 Treatment-Emergent Adverse Events	Safety Analysis Set
15.11.2.2.2	Grade 2, 3, or 4 Treatment-Emergent Adverse Events	Safety Analysis Set
15.11.2.3.1	Treatment-Emergent Treatment-Related Adverse Events	Safety Analysis Set
15.11.2.3.2	Treatment-Emergent Treatment-Related Adverse Events by Preferred Term	Safety Analysis Set
15.11.2.3.3	Grade 3 or 4 Treatment-Emergent Treatment-Related Adverse Events	Safety Analysis Set
15.11.2.3.4	Grade 2, 3, or 4 Treatment-Emergent Treatment-Related Adverse Events	Safety Analysis Set
15.11.4.1	Treatment-Emergent Serious Adverse Events	Safety Analysis Set
15.11.4.3	Treatment-Emergent Treatment-Related Serious Adverse Events	Safety Analysis Set
15.11.5.1	Adverse Events Leading to Premature Discontinuation of Study Drug	Safety Analysis Set
15.11.5.2	Adverse Events Leading or Interruption of Study Drug	Safety Analysis Set
15.11.6.1.1	Hemoglobin (g/dL) and Change from Baseline by Visit	Safety Analysis Set
15.11.6.1.2	Subjects with Postbaseline Hemoglobin < 10 g/dL and < 8.5 g/dL	Safety Analysis Set
15.11.6.1.3	Reticulocytes (x10 ³ /uL) and Change from Baseline by Visit	Safety Analysis Set
15.11.6.1.4	WBC (x10 ³ /uL) and Change from Baseline by Visit	Safety Analysis Set
15.11.6.1.5	Neutrophils (x10 ³ /uL) and Change from Baseline by Visit	Safety Analysis Set
15.11.6.1.6	Lymphocytes (x10 ³ /uL) and Change from Baseline by Visit	Safety Analysis Set
15.11.6.1.7	Platelets (x10 ³ /uL) and Change from Baseline by Visit	Safety Analysis Set
15.11.6.2.1	ALT (U/L) and Change from Baseline by Visit	Safety Analysis Set
15.11.6.2.2	AST (U/L) and Change from Baseline by Visit	Safety Analysis Set
15.11.6.2.3	Total Bilirubin (mg/dL) and Change from Baseline by Visit	Safety Analysis Set
15.11.6.2.4	Alkaline Phosphatase (U/L) and Change from Baseline by Visit	Safety Analysis Set
15.11.6.2.5	Creatinine (mg/dL) and Change from Baseline by Visit	Safety Analysis Set
15.11.6.2.6	Estimated Glomerular Filtration Rate by Cockcroft-Gault (mL/min) and Change from Baseline by Visit	Safety Analysis Set
15.11.6.3	INR and Change from Baseline by Visit	Safety Analysis Set
15.11.6.4.1	Treatment-Emergent Graded Laboratory Abnormalities	Safety Analysis Set
15.11.6.4.2	Treatment-Emergent Grade 3 or 4 Laboratory Abnormalities	Safety Analysis Set
15.11.7.1.1	Systolic Blood Pressure (mmHg) and Change from Baseline by Visit	Safety Analysis Set
15.11.7.1.2	Diastolic Blood Pressure (mmHg) and Change from Baseline by Visit	Safety Analysis Set

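### The <10 g/dL row of the post-baseline hemoglobin table cannot separate pre-existing renal anemia from new cases

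*SAP*

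**What the plan says.** SAP 7.2.1 will summarize "The number of subjects with hemoglobin < 10 g/dL and < 8.5 g/dL at any postbaseline visits", through 30 days after the final dose. SAP Appendix 2 carries this as Table 15.11.6.1.2, "Subjects with Postbaseline Hemoglobin < 10 g/dL and < 8.5 g/dL", with Listing 16.2.8.1.1 under the same title. None of the three mentions the subject's baseline value.

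The protocol makes low baseline values likely:

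- Section 4.2, criterion 5d, sets the entry floor at Screening: "Hemoglobin ≥ 9 g/dL".
- Section 1.6.2 describes a "patient population in which chronic anemia is common".
- Section 1.8 speaks of "patients with advanced renal insufficiency who are usually anemic at baseline".
- Section 5.8.3.2 states: "Patients taking ESAs for anemia related to chronic kidney disease may enter the study".

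Elsewhere the SAP does refer hemoglobin to baseline. Section 7.2.1 also gives baseline values and change from baseline by visit (Table 15.11.6.1.1). Section 7.2.2.1 calls a laboratory abnormality treatment-emergent only if it worsens by at least one grade from baseline (Tables 15.11.6.4.1 and 15.11.6.4.2).

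**The concern.** The <10 g/dL threshold lies above the entry floor, so a subject can satisfy it before the first dose and go on satisfying it with no change. The table then mixes subjects who were already below 10 g/dL with subjects who newly fell below it.

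This has some weight because safety is a primary objective and laboratory abnormalities are among the primary safety endpoints (Protocol 8.1.2). Anemia is also part of the case for Cohort 3: Protocol 1.6.2 presents the absence of ribavirin as a benefit, noting that anemia in Cohort 1 "led to increased epoetin use". A reader who takes the <10 g/dL row as a measure of anemia on LDV/SOF could be misled. SAP 3.2 confirms that there is only one group, so no control row shows the background level.

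ESA use is a second, smaller matter. An ESA started or increased during treatment can hold hemoglobin up, and nothing in this table or its listing would show that.

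**Working it through.** The plan states no expected count for this table, so there is no figure to reproduce.

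**Step 1. Example subjects put through both rules.** Exclusion criterion 6 excludes HIV, so the HIV-negative scale in Protocol Appendix 3 applies: Grade 1 is 10.0 to 10.9, Grade 2 is 9.0 to <10.0, Grade 3 is 7.0 to <9.0 and Grade 4 is <7.0 g/dL. Grades 1 to 3 can also be met by decreases of 2.5, 3.5 and 4.5 g/dL from baseline.

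| Baseline | Worst later value | In <10 row | In <8.5 row | Treatment-emergent (SAP 7.2.2.1) | Newly <10 |
|---|---|---|---|---|---|
| 9.0 | 9.0 | yes | no | no (Grade 2, 2) | no |
| 9.5 | 9.1 | yes | no | no (Grade 2, 2) | no |
| 9.9 | 9.8 | yes | no | no (Grade 2, 2) | no |
| 9.5 | 8.9 | yes | no | yes (Grade 2 to 3) | no |
| 9.9 | 8.6 | yes | no | yes (Grade 2 to 3) | no |
| 9.2 | 8.4 | yes | yes | yes (Grade 2 to 3) | no |
| 10.5 | 9.8 | yes | no | yes (Grade 1 to 2) | yes |

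The first three subjects show no change of grade under the SAP's own rule, yet they are counted exactly like the last one.

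**Step 2. Size per subject.** The planned size of Cohort 3 is 15 (SAP 1.2). One stable subject adds 1/15 = 6.7 points, three add 3/15 = 20.0 and five add 5/15 = 33.3.

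**Step 3. How many subjects? (illustration only).** The documents give no hemoglobin distribution. I assumed a true mean of 10.5 to 12 g/dL, a between-subject SD of 1.3, a visit-to-visit SD of 0.3 to 0.7, a screening value of at least 9, eight post-baseline visits (Weeks 1, 2, 4, 6, 8, 10, 12 and post-treatment Week 4) and no drug effect. Ranges are over the visit-to-visit SD.

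| Assumed mean | Baseline <10 | Expected <10 count of 15, as planned | Of these, baseline >=10 | Any value <8.5 |
|---|---|---|---|---|
| 10.5 | 25.8-27.3% | 6.0-8.6 | 2.2-4.7 | 1.7-12.8% |
| 11 | 17.4-19.1% | 4.3-6.8 | 1.8-4.1 | 0.9-7.9% |
| 11.5 | 10.3-12.4% | 2.7-4.9 | 1.2-3.2 | 0.5-4.3% |
| 12 | 5.5-7.3% | 1.6-3.2 | 0.8-2.3 | 0.2-2.2% |

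Under these assumptions 5.5% to 27.3% of subjects start below 10 g/dL, which is 15 × 0.055 = 0.8 to 15 × 0.273 = 4.1 subjects. In the middle case (mean 11, visit SD 0.5) the planned count is 5.5. Of these, 15 × 0.170 = 2.6 had baseline <10 and 15 × 0.197 = 3.0 had baseline >=10. Splitting by baseline therefore removes a little under half of the no-effect count. The rest is visit-to-visit variation over repeated looks, which no baseline split removes.

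**Step 4. Can other planned outputs supply the split?**

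- Hemoglobin is not among the baseline characteristics in SAP 5.1.
- Table 15.11.6.1.1 gives quartiles and extremes at baseline. These hint at the number below 10 g/dL but do not count it or link it to later values.
- The graded tables cannot isolate a new crossing of 10: a fall from 9.5 to 8.9 is a new Grade 3 in someone already below 10. Nor is 8.5 a boundary on the HIV-negative scale.
- The by-subject hemoglobin listing allows the split, but only by hand.

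**The case against.** The strongest reply is that the count is literally correct and supplementary. The table is titled post-baseline, not treatment-emergent or new, and nothing in the SAP attributes it to the drug. The baseline-referenced work is done elsewhere: change from baseline by visit, graded abnormalities that must worsen from baseline, and adverse event tables in which anemia would appear. Every value is listed by subject, and there is no testing. All of this stands and limits the point to presentation. It does not remove the point, because no planned table gives the number with baseline <10 g/dL or the number newly below 10.

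A second reply concerns the obvious remedy of counting only new crossings. A subject who falls from 9.9 to 8.6 g/dL would then leave the <10 row and still not reach <8.5, so a fall of 1.3 g/dL would appear in neither. A shift table cut only at 8.5 and 10 would miss it too. This is right, and it is why the planned count should stay.

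On ESAs, concomitant medications are summarized by drug and listed by subject and date (SAP 7.3), and the epoetin rise that the protocol reports came from the ribavirin-containing Cohort 1. That also stands. A summary of users, however, cannot distinguish continued use from a start or increase on treatment.

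Stronger readings that a reader might infer are not supported:

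- **That the SAP presents renal anemia as a drug effect.** The title and text do not say so.
- **That both rows are compromised.** A value <8.5 g/dL is at least 0.5 g/dL below the screening floor.
- **That ESA escalation will hide falls in Cohort 3.** The documents allow ESA use but give no such evidence for this cohort.
- **That a known large share of subjects is affected.** An assumed 20% to 40% would be 3 to 6 of 15, but nothing in the documents supports that share over the lower range illustrated above.

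**Conclusion.** The point holds in a limited form. In the <10 g/dL row of Table 15.11.6.1.2, a subject who enters at 9.0 to 9.9 g/dL and does not change cannot be told apart from a new case, and each adds 6.7 points if all 15 planned subjects are in the denominator. This follows from the SAP rule and the entry floor alone and does not depend on the simulation. The number of subjects concerned is unknown; 0.8 to 4.1 of 15 is an illustration under assumed distributions. The <8.5 g/dL row is little affected.

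It is a minor defect in one descriptive safety table, partly covered by the change-from-baseline and graded tables. It does not touch SVR12, and it does not by itself make any safety conclusion wrong.

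**What to change.** In SAP 7.2.1, Table 15.11.6.1.2 and Listing 16.2.8.1.1:

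1. Keep both planned counts.
2. Add the number of subjects with baseline hemoglobin <10 g/dL, and split the <10 g/dL count by baseline (<10 versus >=10 g/dL).
3. Add a shift table of baseline by worst post-baseline hemoglobin, with 9.0 g/dL (an Appendix 3 grade boundary) among the cut-points: for example >=10, 9.0 to <10, 8.5 to <9.0 and <8.5. Alternatively, also show each subject's largest decrease from baseline. Either keeps the fall from 9.9 to 8.6 visible.
4. In the listing, mark subjects whose recorded concomitant medications show an ESA started or increased on treatment, where the database holds this. Do not add a transfusion flag unless transfusions are captured; the Cohort 3 schedule of assessments shows no such item.

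The SAP already works this way elsewhere: ALT normalization is restricted to subjects abnormal at baseline (6.2.2), and diastolic function has a shift table (7.6). The hemoglobin data are already collected. The cost is some extra programming and small denominators within baseline groups, so numbers should be shown beside any percentages. SAP Section 1 has the plan finalized before the SVR12 database; a later change would be documented in the CSR.

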7.2.2. Graded Laboratory Values

The Gilead Grading Scale for Severity of Adverse Events and Laboratory Abnormalities will be used for assignment of toxicity grades to laboratory results for purposes of analysis as Grade 0, Grade 1 (mild), Grade 2 (moderate), Grade 3 (severe) or Grade 4 (potentially life threatening). Grade 0 includes all values that do not meet the criteria for an abnormality of at least Grade 1. For laboratory tests with criteria for both increased and decreased levels, analyses for each direction (ie, increased, decreased) will be presented separately.

7.2.2.1. Treatment-Emergent Laboratory Abnormalities

Treatment-emergent laboratory abnormalities are defined as values that increase at least 1 toxicity grade from baseline at any postbaseline time point, up to and including the date of last dose of study drug plus 30 days. If the relevant baseline laboratory value is missing, any abnormality of at least Grade 1 observed within the time frame specified above will be considered treatment emergent.

7.2.2.2. Summaries of Laboratory Abnormalities

Laboratory data that are categorical will be summarized using the number and percentage of subjects in the study with the given response at baseline and each scheduled postbaseline visit.

The following summaries (number and percentage of subjects) for treatment-emergent laboratory abnormalities will be provided by lab test; subjects will be categorized according to the most severe postbaseline abnormality grade for a given lab test:

- TE Graded laboratory abnormalities
- TE Grade 3 or 4 laboratory abnormalities

For all summaries of laboratory abnormalities, the denominator is the number of subjects with nonmissing postbaseline values up to 30 after last dosing date.

A by-subject listing of treatment-emergent Grade 3 or 4 laboratory abnormalities will be provided by subject ID number and visit in chronological order. This listing will include all test results that were collected throughout the study for the lab test of interest, with all applicable severity grades displayed.

All valid laboratory values will be listed. Values falling outside of the relevant reference range and/or meeting Gilead Grading Scale will be flagged, as appropriate, in the data listings.

7.3. Prior and Concomitant Medications

Medications collected at screening and during the study will be coded using the current version of the World Health Organization (WHO) Drug dictionary. The medications will be categorized as prior or concomitant using the following definitions:

- Prior medications: any medications taken and stopped prior to or on the date of first study drug administration
- Concomitant medications: any medications taken after the date of first study drug administration and up to the last dosing date of study drug

Use of concomitant medications will be summarized by Anatomical Therapeutic Chemical (ATC) drug class Level 2 and preferred name using the number and percentage of subjects. A subject reporting the same medication more than once will be counted only once when calculating the number and percentage of subjects who received that medication. The summary will be ordered alphabetically by ATC medical class and then by preferred term in descending overall frequency within each ATC medical class. For drugs with the same frequency, sorting will be done alphabetically.

For purposes of programming, any medication with a stop date that is on/prior to first dosing date or start date that is after the last dose of any study drug will be excluded from this summary. Otherwise, dates that are completely missing will be included in the summary. If a partial stop date is entered, then the month and year (if day is missing) or year (if day and month are missing) that is prior to the study drug start date will be excluded from the summary. If a partial start date is entered, then the month and year (if day is missing) or year (if day and month are missing) that is after the study drug stop date will be excluded from the summary. Medications with completely missing start and stop dates will be included in the concomitant medication summary, unless otherwise specified. Summaries will be based on the Safety Analysis Set. No formal statistical testing is planned.

A summary of concomitant medications will be provided.

All prior and concomitant medications (other than per-protocol study drugs) will be provided in a by-subject listing sorted by subject ID number and administration date in chronological order.

